2.8 Health outcomes analyses

The health outcome endpoint of this study is subject-reported quality of life.

2.8.1 Health Outcomes Assessments

Quality of life will be assessed using the FACIT-D questionnaire. Patients randomised to receive treatment with octreotide will complete the FACIT-D immediately before receiving the first dose of octreotide. All patients will complete the FACIT-D immediately before the start of treatment with lapatinib and capecitabine, then every three weeks through to withdrawal from the study or the end of the 24 week period of treatment with lapatinib and capecitabine, whichever is sooner.

The FACIT-D (version 4) consists of the FACT-G and a diarrhoea-specific subscale, and measures multidimensional quality of life in patients with cancer. FACT-G includes 27 general questions relating to four subscales: physical wellbeing, social/family wellbeing, emotional wellbeing, functional wellbeing, and the diarrhoea-specific subscale includes 11 questions. Patients assess how true each statement has been for them in the previous 7 days on a 5-point scale ranging from 0 (not at all) to 4 (very much). Higher scores on the FACIT-D scales indicate a better quality of life. In psychometric testing, the FACT/FACIT system has shown good test-retest reliability and sensitivity to change when compared with ECOG performance status.

The following scores will be calculated, using the standard scoring algorithms and methods to deal with missing data:

- Trial Outcome Index (includes diarrhoea subscale)
- Physical subscale,

- Social/Family subscale,
- Emotional subscale
- Functional Wellbeing subscale,
- FACT-G total,
- FACIT-D total.

A by-patient listing of total scores and each of the 4 subscales will be presented. Each of these 7 scores will be listed by visit and treatment group.

2.9 Interim analysis

It was planned to have one formal interim analysis. The results were reviewed by the independent DMC. Based on the interim analysis DMC meeting (09-Sep-2016) it was recommended to stop the trial for futility.

3 Sample size calculation

3.1 Sample size assumptions

It is planned that a total of 140 subjects will be randomised in a 1:1 ratio i.e. 70 subjects in each treatment group. LAP117314 is an exploratory Phase II study, and the sample size is not based on the number of subjects required to achieve a statistically significant pre-specified reduction in the control incidence of diarrhoea. The sample size for this study was based on considerations of cost and feasibility of completing the trial in a timely manner.

The overall incidence of diarrhoea associated with treatment with lapatinib and capecitabine ranges from less than 40% to more than 80% across a number of studies (see Protocol). Only limited data are available on the incidence of diarrhoea with a severity of Grade 2 or more which can be used as a basis for sample size estimation. It is likely that the implementation of active diarrhoea management guidelines will limit the incidence of more severe diarrhoea which develops as a progression from inadequately treated mild diarrhoea. Therefore, a conservative approach has been taken in LAP117314, and data from study EGF111438, which shows the lowest incidence of diarrhoea with a severity of Grade 2 or more (20%), has been used as the basis for the power calculations. In addition, power calculations have been conducted based on a less conservative approach using data from EGF100151, in which diarrhoea management guidelines were not implemented and in which the incidence of diarrhoea with a severity of Grade 2 or more was 32%.

3.2 Sample Size Sensitivity

Based on the results of EGF111438, an incidence of 20% of Grade 2 or higher diarrhoea is assumed for subjects who receive lapatinib and capecitabine with no prophylactic octreotide. The power for the analysis to detect a reduction in the incidence of Grade 2 or higher diarrhoea from 14% to 8% ranges from 69% to 25%, if the assumed incidence in the control group is 20%, using a one-sided test with an alpha level of 0.025 ([Table 3-1](#)).

Table 3-1 Sensitivity of sample size based on 20% control incidence of Grade 2 or more diarrhoea

Incidence, no prophylactic octreotide	20%	20%	20%	20%	20%
Incidence, prophylactic octreotide	6%	7%	8%	10%	12%
Estimated Statistical Power	69%	61%	53%	37%	25%
Subjects per Treatment group	70	70	70	70	70

Based on the results of EGF100151, an incidence of 32% of Grade 2 or higher diarrhoea is assumed for subjects who receive lapatinib and capecitabine with no prophylactic octreotide. The power for the analysis to detect a reduction in the incidence of Grade 2 or higher diarrhoea from 20% to 12% ranges from 82% to 36%, if the assumed incidence in the control group is 32%, using a one-sided test with an alpha level of 0.025 ([Table 3-2](#)) [Table 3-2](#).

Table 3-2 Sensitivity of sample size based on 32% control incidence of Grade 2 or more diarrhoea

Incidence, no prophylactic octreotide	32%	32%	32%	32%	32%
Incidence, prophylactic octreotide	12%	14%	16%	18%	20%
Estimated Statistical Power	82%	72%	60%	48%	36%
Subjects per Treatment group	70	70	70	70	70

Power calculations were performed using nQuery software version 7.0.

3.3 Sample Size Re-estimation

Sample size re-estimation is not planned for this study.

4 Change to protocol specified analyses

Since final CSR will be an abbreviated CSR, not all endpoints will be analysed. [Table 1-3](#) contains reduced list of endpoints as compared to protocol.

Secondary endpoint Patient reported Diarrhoea Management Diary (DMD) is reported using a listing of patients reporting changes in bowel movements from baseline (frequency and/or consistency), recorded in the DMD.

5 Appendix

5.1 Imputation rules

Octreotide will be administered 7 days before the start of treatment with lapatinib and capecitabine and again 28 days later. The primary endpoint is the reduction of treatment-induced diarrhoea for subjects taking lapatinib and capecitabine over 3 cycles. Subjects withdrawing prior to the end of Cycle 3 of lapatinib and capecitabine will be considered to be non-responders. For responder endpoints, subjects withdrawing before the Cycle 4 assessment, i.e. before completing 3 cycles of treatment with lapatinib and capecitabine, will be assumed to be non-responders, and will be included in the denominator when calculating the percentages.

In the event that the study is terminated, all available data will be listed and a review carried out by the study team to assess which statistical analyses are still considered appropriate.

Missing data occurs when any requested data is not provided, leading to blank fields on the collection instrument. These data will be indicated by the use of a “blank” in subject listing displays. Answers such as “Not applicable” and “Not evaluable” are not considered to be missing data and should be displayed as such.

Subjects with the designation of treatment relationship for AEs and SAEs missing will have the worst case assumed to impute the relationship: if relationship to study treatment is missing it will be assumed to be “Yes”.

Imputed partial dates will not be used to derive study day, duration (e.g., duration of adverse events), or elapsed time variables.

With the exception of date of birth on the Demography analysis dataset and exposure end date on the Exposure analysis dataset, imputed dates will also not be stored on datasets.

Imputed dates will not be displayed in listings. However, where necessary, display macros may impute dates as temporary variables for the purpose of sorting data in listings only. In addition partial dates may be imputed for ‘slotting’ data to study time periods or for specific analysis purposes as outlined below.

The partial date imputation will follow ADaM conventions. The ADaM approach is to populate the numeric date variables with the imputed date and add a flag variable to the dataset that indicates the level of imputation.

The flag variable can contain the values: blank, 'D', 'M', 'Y'.

blank: indicates that no imputation was done

D='Day': indicates that the day portion of the date is imputed

M='Month': indicates that the month and day portions of the date are imputed

Y='Year': indicates that the entire date (year, month, and day) is imputed

Example of Date Variables:

XYZD_ - character date variable

XYZDT - numeric date variable

XYZDTFL - flag variable

5.1.1 AE date imputation

Imputations in the adverse events dataset are used for slotting events to the appropriate study time periods and for sorting in data listings.

Dataset	Date	Missing Element	Rule
Adverse Events (AE)	Start Date	day, month,	No Imputation for completely missing dates

Dataset	Date	Missing Element	Rule
		and year	
		day, month	
 • If study treatment start date is missing (i.e. subject did not start study treatment), then set start date = January 1. • Else if study treatment start date is not missing: 
 ◆ If year of start date = year of study treatment start date then 
 - If stop date contains a full date and stop date is earlier than study treatment start date then set start date = January 1. - Else set start date = study treatment start date. ◆ Else set start date = January 1.
		day	
 • If study treatment start date is missing (i.e. subject did not start study treatment), then set start date = 1st of month. • Else if study treatment start date is not missing: 
 ◆ If month and year of start date = month and year of study treatment start date then 
 - If stop date contains a full date and stop date is earlier than study treatment start date then set start date= 1st of month. - Else set start date = study treatment start date. ◆ Else set start date = 1st of month.
	End Date		No imputation for partial end dates will be performed

5.1.2 Concomitant medication and blood and blood supportive care products

Concomitant medication and blood and blood supportive care products are defined as any medications taken 2 weeks prior to the start of octreotide for subjects randomised to octreotide and 2 weeks prior to the start of lapatinib and capecitabine for subjects randomised to no octreotide.

Impute start and end dates for use in derivation of the reference variables concomitant medication start and end relative to treatment and blood and blood supportive care start and end relative to treatment, but do not permanently store the imputed start and end dates in the analysis datasets. The reference variables will be used to differentiate before, during and after for the concomitant medication or blood or blood supportive care start and end dates. The derived time in relation to treatment variables are not needed for reporting of these data.

Dataset	Date	Missing Element	Rule
Concomitant Medication Blood and Blood Supportive Care Products	Start Date	day, month, and year	No Imputation for completely missing dates
		day, month	
 • If study treatment start date is missing (i.e. subject did not start study treatment), then set start date = January 1. • Else if study treatment start date is not missing: 
 ◆ If year of start date = year of study treatment start date then 
 - If stop date contains a full date and stop date is earlier than study treatment start date then set start date = January 1. - Else set start date = study treatment start date. ◆ Else set start date = January 1.
		day	
 • If study treatment start date is missing (i.e. subject did not start study treatment), then set start date = 1st of month. • Else if study treatment start date is not missing: 
 ◆ If month and year of start date = month and year of study treatment start date then 
 - If stop date contains a full date and stop date is earlier than study treatment start date then set start date= 1st of month. - Else set start date = study treatment start date. ◆ Else set start date = 1st of month.
	End Date	day, month, and year	
 • No Imputation for completely missing dates
		day, month	
 • If partial end date contains year only, set end date = earliest of December 31 or date of last contact.
		day	
 • If partial end date contains month and year, set end date = earliest of last day of the month or date of last contact (MSTONE.LCONTD).)

5.1.3 Other imputations

5.1.3.1 Date of birth

Due to data protection rules, only a subject's year of birth (YOB) can be collected, therefore date of birth (DOB) will be imputed as, 30th June YOB, for the calculation of age in the demography dataset

5.1.3.2 Missing exposure end date imputation

In general, completely missing dates are not imputed. However, subjects completing 24 weeks of lapatinib and capecitabine may still be on lapatinib and capecitabine and so may have missing exposure end dates in their last dosing record. Missing exposure end dates for subjects who are still on lapatinib and capecitabine at the time of analysis will be imputed as the date of the End of Study/Withdrawal visit.

For subjects with missing exposure end dates at the time of data cut-off, i.e. for SRT summaries, the exposure end date will be imputed to be the earliest of: the date of the data cut-off, the date of End of Study/Withdrawal visit, or the death date. The imputed exposure end date will be used to calculate cumulative dose and exposure duration. The imputed exposure end date will be stored in the exposure analysis dataset and an exposure end date imputation flag variable will be derived indicating which exposure end date records are imputed. Imputed exposure end dates will also be stored on the study treatment end date variable.

For subjects who have missing end dates in their last exposure record because they are still on lapatinib and capecitabine, the on-therapy indicator variables (time in relation to lapatinib and capecitabine) are assigned to on-therapy for all records where the 'dataset'.date' is after or on the lapatinib and capecitabine start date.

5.1.3.3 Missing death date

For cases when either day is missing or both month and day are missing for the date of death, the following imputation rules will be implemented:

- If only day is missing, then impute max [(1 mmm-yyyy), min(last contact date+1 , cutoff date)].
- If both day and month are missing, then impute max [(1 Jan-yyyy, min (last contact date +1, cutoff date)].

5.2 AEs coding/grading

Adverse events are coded using the Medical dictionary for regulatory activities (MedDRA) terminology.

AEs will be assessed according to the National Cancer Institute Common Terminology Criteria for Adverse Events (NCI-CTCAE) version 4.03.

The NCI-CTCAE represents a comprehensive grading system for reporting the acute and late effects of cancer treatments. NCI-CTCAE grading is by definition a 5-point scale generally corresponding to mild, moderate, severe, life threatening, and death. This grading system inherently places a value on the importance of an event, although there is not necessarily

proportionality among grades (a grade 2 is not necessarily twice as bad as a grade 1). The NCI-CTCAE grade of 5 (death) is not used; rather, ‘fatal’ is collected as AE outcome and death information is also collected on a separate (e)CRF page.

5.3 Statistical models

5.3.1 Analysis of binary data

Analysis of the proportion difference

The null hypothesis of equal proportion of subjects who have a specific event (e.g., the Grade 2 or higher diarrhoea) in the two treatment group will be tested against one-sided alternative.

The statistical hypotheses are:

$$H_0: \delta = 0 \text{ vs. } H_a: \delta < 0,$$

where δ is the difference in proportions of subjects who have a specific event (e.g., the Grade 2 or higher diarrhoea) between two treatment groups, i.e., $\delta = \pi_1 - \pi_2$, where π_1 and π_2 are proportions of subjects who have a specific event in prophylactic octreotide and no prophylactic octreotide group respectively.

The Pearson chi-square test (implemented via SAS procedure FREQ with CHISQ option in the TABLES statement) will be used to test the difference in proportions of subjects who have a specific event between the treatment groups. The two-sided p-value corresponding to the chi-square test will be used which follows a Chi-square distribution with one degree of freedom. The difference in proportions and its corresponding 95% confidence interval will be estimated by using the Wald method (implemented via SAS procedure FREQ with RISKDIFF option in the TABLES statement).

If the sampling assumptions for chi-square test is not met (i.e., the expected values should exceed 5 for all of the table cells.), the exact Pearson chi-square test will be used (implemented via SAS procedure FREQ with the TABLES statement and a CHISQ option in the EXACT statement) for the estimation of the two-sided p-value. The corresponding 95% confidence interval of the difference of proportions between two groups will be estimated by the exact unconditional confidence limits which will be implemented via SAS procedure FREQ with the TABLES statement and RISKDIFF option in the EXACT statement. The approach of exact unconditional confidence limits estimation eliminates nuisance parameters by maximizing the p-value over all possible values of the nuisance parameters [Santner and Snell 1980].

The SAS syntax is specified as follows:

```
PROC FREQ DATA = <input_dataset>;  
  TABLES <treat_var> * <response>/CHISQ RISKDIFF;  
  EXACT CHISQ RISKDIFF;  
RUN;
```

Confidence interval for response rate

Response rate is defined as the percentage of subjects who have a specific event (e.g., experiencing diarrhoea). The $100(1 - \alpha)\%$ confidence interval of a response rate will be

estimated by using exact binomial confidence interval (implemented using SAS procedure FREQ with EXACT statement for one-way table [Clopper and Pearson 1934].

The SAS syntax is specified as follows:

```
PROC FREQ DATA = <input_dataset>;  
  BY <treat_var>;  
  TABLES <response>/BINOMIAL (EXACT) ;  
RUN;
```

where treat_var = treatment group
response = response (e.g., diarrhoea)

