2.8	Health outcomes analyses	32
2.8.1	Health Outcomes Assessments.....	32
2.9	Interim analysis	33
3	Sample size calculation.....	33
3.1	Sample size assumptions.....	33
3.2	Sample Size Sensitivity.....	33
3.3	Sample Size Re-estimation	34
4	Change to protocol specified analyses.....	34
5	Appendix.....	34
5.1	Imputation rules	34
5.1.1	AE date imputation.....	35
5.1.2	Concomitant medication and blood and blood supportive care products	36
5.1.3	Other imputations	38
5.2	AEs coding/grading.....	38
5.3	Statistical models	39
5.3.1	Analysis of binary data.....	39
5.3.2	Analysis of time to events data.....	40
6	Reference	40

List of abbreviations

AE	Adverse event
ATC	Anatomical Therapeutic Classification
CSR	Clinical Study report
CTC	Common Toxicity Criteria
CTCAE	Common Terminology Criteria for Adverse Events
DMC	Data Monitoring Committee
DMD	Diarrhoea Management Diary
eCRF	Electronic Case Report Form
FACIT-D	Functional Assessment of Chronic Illness therapy-Diarrhoea
FACT-G	Functional Assessment of Cancer Therapy-General
MedDRA	Medical Dictionary for Drug Regulatory Affairs
NCI	National Cancer Institute
PRO	Patient-reported Outcomes
RECIST	Response Evaluation Criteria in Solid Tumors
SAP	Statistical Analysis Plan
SOC	System Organ Class

1. Introduction

This statistical analysis plan (SAP) describes analyses required for a Clinical Study Report (CSR) to support a publication of study LAP016A2410, a randomised, multicentre, open label, phase II study of Prophylactic Octreotide to prevent or reduce the frequency and severity of diarrhoea in subjects receiving Lapatinib with Capecitabine for the treatment of metastatic breast cancer. This is a phase II study to evaluate the efficacy, safety [REDACTED] of prophylactic octreotide compared to no octreotide using a parallel group, open label, randomised study design.

As first interim analysis results showed study is futile and no patients will be recruited in the study. For final analysis abbreviated CSR will be done and it will include reduced analyses as compared to planned analyses in the protocol.

As planned in the protocol an interim analysis was performed after 62 patients enrolled using a cut-off date (30-Mar-2016) and an interim database lock on 16-Aug-2016. As the interim analysis results showed study was futile the DMC recommended to stop the study. Per protocol no further patients were enrolled in the study per IA cut-off.

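### In sparse tables the SAP's exact interval for the risk difference, read as inverting the raw difference, is typically 30–44% wider than a score-based exact interval and can contradict the test beside it

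*SAP*

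**What the plan says.** SAP 5.3.1 tests the difference with a Pearson chi-square test. For the difference in proportions, the "confidence interval will be estimated by using the Wald method". The condition for this is that "the expected values should exceed 5 for all of the table cells". If it fails, the p-value comes from the exact Pearson test and the interval "will be estimated by the exact unconditional confidence limits". The code is `EXACT CHISQ RISKDIFF`, with no score option. The text cites Santner and Snell and says the nuisance parameter is removed by maximising the p-value.

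The rule was written for the full trial: "It is planned that a total of 140 subjects will be randomised in a 1:1 ratio i.e. 70 subjects in each treatment group". SAP section 1 reports that "an interim analysis was performed after 62 patients enrolled", after which the trial stopped for futility.

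For the primary ITT endpoint, SAP 2.5.2.1 and 2.5.3 count a withdrawal up to the Cycle 4 visit as a Grade 2 or higher event, and the m-ITT analysis does the same. There is no such imputation in the per-protocol analysis (2.5.3, 2.5.4) or for Grade 2 or higher over the whole treatment period (2.5.3). Neither of these has a test. Grade 3 or higher over the whole period follows the methods of 2.5.2 (SAP 2.6.1.1).

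**The concern.** At 70 per arm the exact branch would almost never have been used. At about 31 per arm it becomes a live option, so its properties matter. Limits that invert the raw difference are very conservative. At equal arm sizes they depend only on the difference in event counts, so 2 v 6 and 3 v 7 give the same interval (about -38 to +13 points), because the worst-case nuisance rate sets the width.

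After a futility stop, the estimate and its interval are the main lasting result, and SAP section 1 says the report supports a publication. An interval much wider than it need be blurs how much benefit or harm the data exclude. The reader may also see a significant p-value beside an interval that contains zero.

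**Working it through.** **Inputs.**
- 62 patients (SAP section 1). An even split of 31 and 31 is my assumption.
- Control rates from SAP 3.2: "an incidence of 20% of Grade 2 or higher diarrhoea is assumed for subjects who receive lapatinib and capecitabine with no prophylactic octreotide", with octreotide at 6–12%; and "an incidence of 32% of Grade 2 or higher diarrhoea is assumed for subjects who receive lapatinib and capecitabine with no prophylactic octreotide", with octreotide at 12–20%.
- No withdrawal rate is given, so a range is shown.
- Grade 3 or higher control rates: 6% (Protocol Table 3) and (31+2)/210 = 16% (Protocol Table 2).

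**The plan's own power figures.** A pooled-variance chi-square calculation at 70 per arm, "using a one-sided test with an alpha level of 0.025", gives 69.6/61.6/53.5/38.0/25.0% and 82.2/72.0/60.3/48.1/36.5%. The SAP states 69/61/53/37/25% and 82/72/60/48/36%, so the rates and the test are understood correctly.

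**When the switch occurs.** With t events in total and equal arms, each expected event count is 31t/62 = t/2. This exceeds 5 only if t is 11 or more, so 10 or fewer events trigger the exact branch.

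**Width for 2/31 (octreotide) v 6/31 (control).** The difference is -4/31 = -12.9 points.

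| Interval | Limits | Width |
|---|---|---|
| Wald: -0.129 ± 1.96 × √(0.0645×0.9355/31 + 0.1935×0.8065/31) | -0.293 to 0.035 | 0.328 |
| Miettinen-Nurminen | -0.312 to 0.045 | 0.357 |
| Exact, score-standardised | -0.320 to 0.045 | 0.366 |
| Exact, raw difference | -0.380 to 0.135 | 0.515 |

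The exact intervals invert two one-sided 0.025 tests, with the p-value maximised over the nuisance rate. The ratio is 0.515/0.366 = 1.41. It is 1.38 for 2 v 7 and 1.31 for 4 v 6. Typical tables with 7 to 10 events give 30–44% excess width. Coverage of the raw version is 99.5–99.9% at the 20% control rate.

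**Agreement with the exact Pearson test.**
- 0 v 6: p=0.024; raw interval -0.439 to 0.071; score-exact -0.378 to -0.058.
- 1 v 9: p=0.012; raw interval -0.497 to 0.006; score-exact -0.448 to -0.075.

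**Jump at the threshold.** 3 v 7 (10 events) gives an exact width of 0.515. 4 v 7 (11 events) gives a Wald width of 0.377.

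**Probability of the switch, primary ITT endpoint.** This is the binomial probability of 10 or fewer events. If a fraction w in each arm withdraws independently of diarrhoea, each rate p becomes p + w(1-p).

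| Control rate | w | Probability across the planned octreotide rates |
|---|---|---|
| 20% | 0 | 59–83% |
| 20% | 5% | 27–48% |
| 20% | 10% | 8–18% |
| 20% | 15% | 2–5% |
| 32% | 0 | 4.5–16% |

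At 70 per arm with no withdrawals it is 1.8% or less. Splits from 29/33 to 33/29 move the no-withdrawal figures by about 3 points or less.

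**Grade 3 or higher, no imputation.** At 6% control the probability is above 99%. At 16% control it is 59% with no octreotide effect and 88% if octreotide halves the rate (assumed effects).

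**Wald branch.** Enumerated coverage at 31 per arm over the ten planning pairs is 93.1–94.4%, against 93.8–95.2% for Miettinen-Nurminen. Restricted to tables with 11 or more events, Wald coverage is 90.4–94.4% at 20% control and about 94% at 32%. The 90.4% belongs to the 20% v 6% pair, where Wald is used only 17% of the time.

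**The case against.** The strongest reply is that the exact branch is unlikely in the primary analysis. Protocol 4.3.2 requires subjects who permanently stop lapatinib and capecitabine to be withdrawn, and progression is a listed reason. The Protocol 1.1 median PFS of 27.1–28.6 weeks, taken as exponential, implies 1 - 0.5^(9/27.1) = 21% to 1 - 0.5^(9/28.6) = 20% progressed or dead by week 9. If all of them were imputed as events, the switch probability would fall below 1%. Protocol 4.3.3, however, treats progression as completion, so this is one end of a range. A reader might infer that the wide interval is likely at the planning rates generally. For the primary endpoint the documents do not support that: it needs the 20% control rate and almost no withdrawals. The reply does not reach the analyses without imputation.

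It is also fair to say that conservative limits are valid and pre-specified, and that no decision turns on them because the trial has already stopped. This stands: the loss is of precision, not of validity. Nor does the small Wald shortfall make that branch seriously wrong in an exploratory study.

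Finally, score-based limits have their own disagreement with the exact test. For 0 v 4 (p=0.11) and 2 v 8 (p=0.08) the Miettinen-Nurminen upper limit is -0.010 in both cases, and the score-exact limits also just exclude zero. This stands as a small cost of the change.

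**Conclusion.** The point holds for the sparse branch. Where that branch is used, its interval is typically 30–44% wider than a valid score-based exact interval and can include zero beside a significant exact test. For the primary ITT endpoint it is a possibility whose size depends on the control rate and the number of withdrawals. It matters most for Grade 3 or higher diarrhoea, for Grade 2 or higher over the whole period, and for the per-protocol analysis. In the last two no test is run, so an interval would be the only inferential output. The per-protocol set is also analysed only if it is no more than 95% of ITT, so it would be smaller than 31 per arm.

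The futility conclusion is unaffected. The finding rests on three assumptions: an even split of the 62 patients; that the code as written inverts the raw difference, which fits the citation and the missing score option but is not stated; and that the whole-period Grade 3 or higher summary carries no imputation and does report the interval under 2.5.2.

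**What to change.** In the sparse branch of SAP 5.3.1, specify score-standardised exact unconditional limits by adding the score method to the RISKDIFF request in the EXACT statement, and name the inverted statistic in the text. Preferably also replace Wald with the Miettinen-Nurminen interval in the non-sparse branch, so that both branches are score-based and one extra event no longer changes the width sharply. Keep the Pearson and exact Pearson tests as planned.

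The programming cost is a change of options in the same procedure. The statistical cost is that a score-based interval will occasionally exclude zero when the exact p-value is above 0.05. The report should therefore say that interval and test use different methods. If the SAP is locked, give the score-based interval as a supplementary result and identify it as a deviation in the CSR, as SAP 2.1.2 provides.
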